4.3. Lifestyle and/or Dietary Restrictions

4.3.1. Contraception Requirements

4.3.1.1. Female Subjects

Female subjects must not become pregnant for 2 weeks prior to dosing and for 60 days after and so must be sexually inactive by abstinence or use contraceptive methods with a failure rate of <1%. Female subjects with same sex partners (when this is their preferred and usual lifestyle) are not required to be abstinent or to use contraception.

Abstinence

Sexual inactivity by abstinence must be consistent with the preferred and usual lifestyle of the subject. Periodic abstinence (e.g. calendar, ovulation, symptothermal, post-ovulation methods) and withdrawal are not acceptable methods of contraception.

Contraceptive Methods with a Failure Rate of <1%

- Oral contraceptive, either combined or progestogen alone
- Injectable progestogen
- Implants of etonogestrel or levonorgestrel
- Estrogenic vaginal ring
- Percutaneous contraceptive patches
- Intrauterine device (IUD) or intrauterine system (IUS) that meets the <1% failure rate as stated in the product label
- **Documented** male partner sterilization prior to **the female subject's entry** into the study, and this male is the sole partner for that subject. For this definition, “documented” refers to the outcome of the investigator's/designee's review of the subject's medical history for study eligibility, as obtained via a verbal interview with the subject or from the subject's medical records.
- Male condom combined with a female diaphragm, either with or without a vaginal spermicide (foam, gel, cream or suppository).

NOTE: These allowed methods of contraception are only effective when used consistently, correctly and in accordance with the product label. The investigator is responsible for ensuring subjects understand how to properly use these methods of contraception.

4.3.1.2. Male Subjects

Male subjects with female partners of child-bearing potential must use one of the following contraceptive methods for 2 weeks prior to dosing and for 60 days after the last dose of study treatment:

- Condom plus partner use of a highly effective contraceptive (see list in Section 4.3.1.1).
- Abstinence, defined as sexual inactivity consistent with the preferred and usual lifestyle of the subject. Periodic abstinence (e.g. calendar, ovulation, symptothermal, post-ovulation methods) and withdrawal are not acceptable methods of contraception

4.3.2. Meals and Dietary Restrictions

4.3.2.1. Alcohol

- During the dosing session, patients will abstain from alcohol for 24 hours prior to the start of dosing until collection of the final pharmacokinetic and or pharmacodynamic sample during the dosing session and around each visit.

4.3.2.2. Activity

Patients will abstain from strenuous exercise for 48 hours prior to each blood collection for clinical laboratory tests. Patients may participate in light recreational activities during study visits (e.g., watch television, read).

4.3.2.3. Travel

Patients will also be advised to refrain from travelling to countries where there is a high incidence of infectious diseases within the first six months from start of treatment.

4.4. Screen and Baseline Failures

Screen failures are defined as subjects who consent to participate in the clinical trial but are not subsequently randomized. To ensure transparent reporting of screen failure data (in order to meet the Consolidated Standards of Reporting Trials (CONSORT) publishing requirements), and respond to queries from Regulatory authorities, a minimal set of screen failure information is required including:

- Demography,
- Reason for screen failure,
- Eligibility criteria,
- Serious adverse events.

4.5. Withdrawal Criteria and Procedures

A patient may withdraw from study treatment at any time at his/her own request, or may be withdrawn at any time at the discretion of the investigator for safety, behavioural or administrative reasons. Subjects who withdraw may be replaced to ensure that data on 40 subjects are obtained.

The decision on whether to replace the patient will be based on the reason for premature discontinuation, as described in [Table 3](#).

Table 3 Patient replacement

Patients will be replaced if:	
 • The reason for withdrawal was not treatment related (e.g. patient withdrew consent for personal reasons). • Adverse event judged unrelated to treatment
Patients will not be replaced if:	
 • There is a lack of tolerability to treatment. • Individual or group stopping criteria are met. • Significant changes in any of the safety assessments (e.g. ECG, vital signs, laboratory tests, etc).

Decisions regarding patient replacement will be made in consultation with the Medical Monitor who will discuss with GSK.

Subjects that have received treatment and who withdraw should continue to undergo all safety assessments as per protocol including PK sampling, if possible. However, efficacy (hyperglycaemic clamp and MMTT) pharmacodynamic (PD) assessments may not always be performed. The need to perform PD assessments will be agreed on a case-by-case basis. The date of withdrawal must be recorded in the eCRF. If the patient agrees they will follow the original scheduled visit plan after withdrawal.

Refer to Section [5.3.1](#) for dose adjustment/stopping criteria.

Liver chemistry threshold stopping criteria have been designed to assure patient safety and to evaluate liver event etiology (in alignment with the FDA premarketing clinical liver safety guidance). See Section [5.3.4](#) for details.

4.6. Patient Completion

A completed patient is one who has completed Month 24.

The end of the study is defined as the last patient's last visit Month 24 or at final follow-up.

5. STUDY TREATMENT

5.1. Investigational Product and Other Study Treatment

	Study Treatment	
Product name:	GSK2136525: Otelixizumab Concentrated Solution for Infusion, 5 mg/mL	Placebo (0.9% w/v Sodium Chloride)
Dosage form:	Concentrated Solution for Infusion	Solution for Injection
Unit dose strength(s)/Dosage level(s):	Unit dose strength: 5 mg/mL provided as 1 mL solution per vial to be diluted to 0.1 mg/mL in 0.9% sodium chloride Dosage levels: variable	0.9% w/v Sodium Chloride/ Placebo level variable
Route/ Administration/ Duration:	Intravenous infusion via syringe pump; using only the infusion kits supplied by CRO/GSK, administration duration varies	Intravenous infusion via syringe pump; using only the infusion kits supplied by CRO/GSK, administration duration varies
Dosing instructions:	Study medication will be diluted to 0.1 mg/mL in 0.9% w/v sodium chloride to prepare otelixizumab solution for Infusion, 0.1 mg/mL. The 0.1 mg/mL solution is administered by intravenous infusion using a syringe pump and an in-line 0.2 micron filter by study personnel following specified regimens	0.9% w/v sodium chloride administered by intravenous infusion in the same manner as the active by study personnel following specified regimens
Manufacturer/ source of procurement:	Study medication supplied by GSK 0.9% w/v sodium chloride sourced locally by site	0.9% w/v sodium chloride sourced locally by site

5.2. Treatment Assignment

Patients will be assigned to receive either otelixizumab or matching placebo (4:1 ratio), prior to the start of dosing in each cohort by utilizing RAMOS (GSK's Registration and Ordering System). The randomization schedule utilized by RAMOS will be provided by Clinical Statistics (CS), using internal validated software. Once a randomisation number has been assigned it must not be re-assigned.

A description of each regimen is provided in [Table 4](#):

Table 4 Treatment Assignment

Treatment	Cohort	Treatment Description	Daily Dose of Otelixizumab (mg)
A	1	Otelixizumab 9 mg	1.5
B	2	Otelixizumab 18 mg	3
C	3	Otelixizumab 27 mg	4.5
D	4	Otelixizumab 36 mg	6
P	1-4	Placebo	N/A

5.3. Patient Specific and Dose Escalation Stopping Criteria

5.3.1. Cytokine Release Syndrome Stopping Criteria

Cytokine Release Syndrome (CRS) experienced during the 6 days of dosing will be monitored specifically by the investigator according to the grading system presented in [Table 5](#) and Section 7.1.5. In-stream real time data review will be utilised, so as to limit patient exposure unnecessarily, if stopping criteria are met.

Table 5 CRS AE Grading System

Adverse Event	Grade 1	Grade 2	Grade 3	Grade 4	Grade 5
Headache	Mild pain	Moderate pain; limiting instrumental ADL	Severe pain; limiting self care ADL	-	-
Fever	38.0 - 39.0 degrees C	>39.0 - 40.0 degrees C	>40.0 degrees C for <=24 hrs	>40.0 degrees C for >24 hrs	Death
Vomiting	1 - 2 episodes (separated by 5 minutes) in 24 hrs	3 - 5 episodes (separated by 5 minutes) in 24 hrs	>=6 episodes (separated by 5 minutes) in 24 hrs	Life-threatening consequences; urgent intervention indicated	Death
Diarrhoea	Increase of <4 stools per day over baseline.	Increase of 4 - 6 stools per day over baseline.	Increase of >=7 stools per day over baseline; incontinence; limiting self care ADL	Life-threatening consequences; urgent intervention indicated	Death
Hypotension	Asymptomatic, intervention not indicated	Non-urgent medical intervention indicated	Urgent medical intervention indicated	Life-threatening and urgent intervention indicated	Death
Chills	Mild sensation of cold; shivering; chattering of teeth	Moderate tremor of the entire body; narcotics indicated	Severe or prolonged, not responsive to narcotics	-	-
Nausea	Loss of appetite without alteration in eating habits	Oral intake decreased without significant weight loss, dehydration or malnutrition	Inadequate oral caloric or fluid intake.	-	-

Adverse Event	Grade 1	Grade 2	Grade 3	Grade 4	Grade 5
Arthralgia	Mild pain	Moderate pain; limiting instrumental ADL	Severe pain; limiting self care ADL	-	-
Myalgia	Mild pain	Moderate pain; limiting instrumental ADL	Severe pain; limiting self care ADL	-	-

ADL= Activities of daily living

Pre-specified CRS individual patient and study dosing stopping criteria are presented in [Table 6](#) and should be followed by the Investigator.

- If individual patient criteria are met: Treatment for that patient will be stopped immediately, will not be restarted, and the patient will be followed up as per protocol.
- If study dosing stopping criteria are met: In addition to the individual patient instruction above, no further patients will be dosed within the cohort currently being investigated and no further dose escalation will occur; patients who have been dosed will be followed up as per protocol.

The symptoms in [Table 6](#) have been classified as objective and subjective endpoints as follows:

Objective Endpoints: Fever, Diarrhoea, Vomiting, Hypotension

Subjective Endpoints: Headache, Chills, Nausea, Arthralgia, Myalgia

Based on the above classification four possible outcomes have been defined where dosing would be stopped, as described in [Table 6](#):

Table 6 Stopping Criteria for CRS-Adverse Events

Scenario	NCI-CTC Scores	Individual Subject Criteria
I	2 objective endpoints \geq grade 2 OR Fever, vomiting, or diarrhoea \geq grade 2 persisting >48 hours despite treatment	Stop treatment
II	1 objective endpoint \geq grade 2 AND 
 • 2 subjective endpoints (except chills) \geq grade 3 OR • 1 subjective endpoint \geq grade 3 and Chills \geq grade 2 	Stop treatment
III	Three subjective endpoints \geq grade 3 (except if one subjective endpoint is Chills, which only needs to be \geq grade 2)	Stop treatment
IV	1 objective endpoint \geq grade 4	Stop treatment
Study Dosing Stopping Criteria: 
 • If ≥ 3 subjects on otelixizumab treatment within a cohort meet individual Stopping Criteria I-III detailed above. 
Or
 
 • If 1 subject on otelixizumab treatment within a cohort meet individual Stopping Criteria IV. 		

Note: in order to meet individual stopping criteria, the reported objective or subjective endpoints must be of different types during one 24 hour dosing period for any of the scenarios involving more than one endpoint.

5.3.2. EBV Stopping Criteria

Three parameters as described in [Table 7](#) will be used to assess EBV reactivation at a patient level to determine dose escalation:

Table 7 Parameters used to Assess EBV Reactivation

Parameter	Criteria
Clinical Symptoms of Mononucleosis	Fever, fatigue, malaise, myalgia, pharyngodynia, lymphadenopathy
Change in Viral Load	EBV by PCR more than 10,000 copies per 10 ⁶ peripheral blood mononuclear cells
Change in Serology	Emergence of IgM for EBV on otherwise EBV-IgG positive patients

Table 8 shows the possible combinations of the three EBV parameters that will be used to assess whether the patient has clinical EBV reactivation for the purpose of the stopping criteria. The assessment will be conducted for each subject at approximately 6 weeks post first active dose.

Table 8 Assessment of EBV Reactivation

Clinical Signs of Mononucleosis	Serology	Virology	EBV Reactivation
+	-	-	NO*
+	+	+	YES
+	+	-	YES
+	-	+	YES
-	-	-	NO
-	+	+	NO
-	+	-	NO
-	-	+	NO

*Other causes of mononucleosis should be checked

There will be ongoing reviews of safety data throughout the trial progression and on completion of each cohort.

[figure not shown]
If $\geq 3/8$ patients on active treatment within a cohort develop symptoms of clinical EBV reactivation as described above, the dosing will be stopped and no further dosing will be carried out on any other patients; patients who have been dosed will be followed up as per protocol.

Patient history will be assessed for symptoms of infectious mononucleosis, and spontaneous AE reporting will be implemented for assessing clinical EBV reactivation.

5.3.3. Assessment of Cytokine Release Syndrome & EBV Stopping Criteria

A summary schematic for dose escalation criteria based on CRS & EBV (refer to sub-Sections in Section 5.3 for criteria) are presented in Figure 5:

Figure 5 Dose Escalation Schematic

¹: As defined in Table 6

²: As defined in Table 7

5.3.4. Liver Chemistry Stopping Criteria

Liver chemistry threshold stopping criteria have been designed to assure patient safety and to evaluate liver event etiology (in alignment with the FDA premarketing clinical liver safety guidance).

Study treatment will be stopped for a patient if the following liver chemistry stopping criteria is met:

1. ALT \geq 3xULN and bilirubin \geq 2xULN
NOTE: serum bilirubin fractionation should be performed if testing is available. If fractionation is unavailable, urinary bilirubin is to be measured via dipstick (a measurement of direct bilirubin, which would suggest liver injury).

2. ALT \geq 5xULN.
3. ALT \geq 3xULN if associated with symptoms (new or worsening) believed to be related to hepatitis (such as fatigue, nausea, vomiting, right upper quadrant pain or tenderness or jaundice) or believed to be related to hypersensitivity (such as fever, rash or eosinophilia).
4. ALT \geq 3xULN persists for \geq 4 weeks.
5. ALT \geq 3xULN and cannot be monitored weekly for 4 weeks.

Subjects with ALT \geq 3xULN **and** $<$ 5xULN **and** bilirubin $<$ 2xULN, who do not exhibit hepatitis symptoms or rash, can continue study treatment as long as they can be monitored weekly for 4 weeks.

NOTE: Refer to [Appendix 1](#), for details of the required assessments if a subject meets any of the above criteria.

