12. APPENDICES

12.1. Appendix 1: Liver Safety Process

The procedures listed below are to be followed if a patient meets any of the liver chemistry stopping criteria defined in Section 5.3.4

- Immediately withdraw the patient from study treatment if the 6 day treatment period has not been completed. Patients will continue to be monitored for safety as per protocol
- Notify the GSK medical monitor within 24 hours of learning of the abnormality to confirm the patient's study treatment cessation and follow-up.
- Complete the "Safety Follow-Up Procedures" listed below.
- Complete the liver event case report forms. If the event also meets the criteria of an SAE (see Section 7.1.4), the SAE data collection tool will be completed separately with the relevant details.
- Upon completion of the safety follow-up withdraw the patient from the study unless further safety follow up is required.
- Do not re-challenge with investigational product

Safety Follow-Up Procedures for patients with ALT $\geq 3xULN$ and bilirubin $\geq 2xULN$ (>35% direct); or ALT $\geq 3xULN$ and INR¹ >1.5 [Stopping Criteria #1]:

- This event is considered an SAE (see Section 7.1.4). Serum bilirubin fractionation should be performed if testing is available. If fractionation is unavailable, urinary bilirubin is to be measured via dipstick (a measurement of direct bilirubin, which would suggest liver injury).
- Make every reasonable attempt to have the patients return to the clinic (within 24 hours) for repeat liver chemistries, additional testing and to be monitored closely (with specialist or hepatology consultation recommended).
- Monitor patients twice weekly until liver chemistries (ALT, AST, alkaline phosphatase, bilirubin) resolve, stabilize or return to within baseline values.

Safety Follow-Up Procedures for patients with ALT $\geq 5xULN$ or ALT $\geq 3xULN$ who have hepatitis symptoms or rash, can't be monitored for 4 weeks or have elevations that persist ≥ 4 weeks [Stopping Criteria #2 - #5]:

- Make every reasonable attempt to have the patient return to the clinic within 24-72 hrs for repeat liver chemistries and additional testing.

¹ INR testing not required per protocol and the threshold value does not apply to subjects receiving anticoagulants.

- Monitor patients weekly until liver chemistries (ALT, AST, alkaline phosphatase, bilirubin) resolve, stabilize or return to within baseline values.

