Safety Follow-Up Procedures for patients with ALT \geq 3xULN and $<$ 5xULN and bilirubin $<$ 2xULN, who do not exhibit hepatitis symptoms or rash:

- Notify the GSK medical monitor within 24 hours of learning of the abnormality to discuss patient safety.
- Patient can continue study treatment if liver chemistries (ALT, AST, alkaline phosphatase, bilirubin) can be monitored weekly for up to 4 weeks.
- If at any point these patients meet the liver chemistry stopping criteria (outlined in Section 5.3.4), immediately withdraw study treatment, perform additional testing and continue safety follow-up until liver chemistries resolve, stabilize or return to baseline values.
- After 4 weeks of monitoring, if ALT $<$ 3xULN and bilirubin $<$ 2xULN, patients must be monitored twice monthly until liver chemistries normalize or return to within baseline values.

Additional Follow-Up Procedures for patients who meet *any* of the stopping criteria:

[figure not shown]
- Viral hepatitis serology including:
 - Hepatitis A IgM antibody;
 - Hepatitis B surface antigen and Hepatitis B Core Antibody (IgM);
 - Hepatitis C RNA;
 - Cytomegalovirus IgM antibody;
 - Epstein-Barr viral capsid antigen IgM antibody (or if unavailable, obtain heterophile antibody or monospot testing);
 - Hepatitis E IgM antibody.
- Blood sample for pharmacokinetic (PK) analysis, obtained within 7 days of last dose. Record the date/time of the PK blood sample draw and the date/time of the last dose of study treatment prior to blood sample draw on the eCRF. If the date or time of the last dose is unclear, provide the patients's best approximation. If the date/time of the last dose can not be approximated OR a PK sample can not be collected in the time period indicated above, **do not obtain a PK sample**. Instructions for sample handling and shipping are included in the SRM.
- Serum creatine phosphokinase (CPK) and lactate dehydrogenase (LDH).
- Fractionate bilirubin, if total bilirubin \geq 2xULN.
- Assess eosinophilia
- Record the appearance or worsening of clinical symptoms of hepatitis (fatigue, nausea, vomiting, right upper quadrant pain or tenderness, fever, rash or eosinophilia) as relevant on the AE eCRF

- Record use of concomitant medications, acetaminophen, herbal remedies, other over the counter medications, or putative hepatotoxins on the Concomitant Medications eCRF.
- Record alcohol use on the Liver Events eCRF.

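### Appendix 1 lists ALT ≥3xULN with INR >1.5 under liver stopping criterion 1 and as an SAE, but neither Section 5.3.4 nor Appendix 1's own permission to keep dosing has an INR condition (minor)

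*Protocol*

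**What the plan says.** Protocol Section 5.3.4 lists five liver stopping criteria. Criterion 1 is ALT ≥3xULN together with bilirubin ≥2xULN. INR appears in none of the five. The section then says that subjects with ALT from 3 to below 5xULN and bilirubin below 2xULN "who do not exhibit hepatitis symptoms or rash, can continue study treatment as long as they can be monitored weekly for 4 weeks".

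Appendix 1 (Section 12.1) opens with this sentence: "The procedures listed below are to be followed if a patient meets any of the liver chemistry stopping criteria defined in Section 5.3.4". The first procedure under it is: "Immediately withdraw the patient from study treatment if the 6 day treatment period has not been completed". A later heading sets out follow-up for the bilirubin combination or, as an alternative, for ALT ≥3xULN with INR ">1.5 [Stopping Criteria #1". The first bullet under that heading says "This event is considered an SAE (see Section 7.1.4". A footnote adds that the protocol does not require INR and that the threshold is waived for anyone on anticoagulants.

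Further on, Appendix 1 has a separate block for ALT from 3 to below 5xULN, bilirubin below 2xULN and no hepatitis symptoms or rash. It says: "Patient can continue study treatment if liver chemistries (ALT, AST, alkaline phosphatase, bilirubin) can be monitored weekly for up to 4 weeks". INR is not mentioned there.

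**The concern.** The same numbered criterion has different content in two current parts of the protocol. One group of patients meets the version with the INR arm but not the version without it: ALT in the 3 to <5xULN band, bilirubin below 2xULN, no symptoms, no anticoagulant, weekly monitoring possible, and an INR that happened to be measured and exceeded 1.5. For them the text gives conflicting signals on dosing and on SAE status.

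What is at stake is a safety rule. The risk table in Protocol Section 3.4 links the earlier 48-64 mg regimens to abnormal liver chemistry and names the liver withdrawal and stopping criteria as part of the mitigation. A raised INR alongside raised ALT is a sign of impaired liver function. SAE status also decides whether the 24-hour report in Section 7.1.8 applies, and whether the case counts as a liver stopping event could bear on the liver outputs foreseen in SAP Section 7.1.

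**Working it through.** No statistical figure is involved, so the check applies each rule to the same patient.

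**Rules** (ALT and bilirubin in multiples of ULN)

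- A, stop under 5.3.4: (ALT ≥3 and bilirubin ≥2), or ALT ≥5, or ALT ≥3 with symptoms, or ALT ≥3 for at least 4 weeks, or ALT ≥3 without the possibility of weekly monitoring.
- B, may continue under 5.3.4: ALT ≥3 and <5, bilirubin <2, no hepatitis symptoms or rash, weekly monitoring possible.
- C, INR arm in the Appendix 1 heading: ALT ≥3 and INR >1.5, not on anticoagulants.
- D, may continue under Appendix 1: same ALT, bilirubin, symptom and monitoring conditions as B.

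**Illustrative profile:** bilirubin 1.0, no symptoms, under 4 weeks, weekly monitoring possible, no anticoagulant.

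| ALT | INR | A: stop | B: may continue | C: INR arm met | D: may continue | Conflict |
|---|---|---|---|---|---|---|
| 3.0, 4.0 or 4.9 | 1.6 | no | yes | yes | yes | yes |
| 3.0, 4.0 or 4.9 | 1.5 | no | yes | no | yes | no |
| 5.0 | 1.6 | yes | no | yes | no | no |

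If bilirubin is ≥2 and ALT ≥3, criterion 1 in 5.3.4 is met whatever the INR. The conflict is therefore confined to ALT 3 to <5xULN, bilirubin <2xULN and INR >1.5. For dosing, it matters only within the 6 dosing days.

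**Do the cross-references settle it?** Four places direct the reader to 5.3.4, which has no INR arm: Section 4.5, the note in Section 6.4.4.2, the opening of Appendix 1, and the later-stop bullet in Appendix 1, which reads "If at any point these patients meet the liver chemistry stopping criteria (outlined in Section 5.3.4), immediately withdraw study treatment". In the other direction, 5.3.4 refers to Appendix 1 "for details of the required assessments if a subject meets any of the above criteria", and this patient meets none of them. So neither route brings the INR arm into the dosing rule.

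**Section 7.1.4(g).** In the text available, the bilirubin branch ends on a conjunction with nothing after it, while a note about INR remains. Text may have been lost there, so I do not count this as a second mismatch.

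**How often could it arise?** Section 6.4.4.2 lists 16 clinical chemistry entries (total and direct bilirubin counted as one, the Day -1 CRP left out). INR is not among them, nor is it in the Appendix 1 work-up for patients who meet a stopping criterion. The documents hold no INR data, so no frequency can be given.

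**The case against.** A reader might infer a clean split, in which 5.3.4 lets the patient continue and Appendix 1 orders a stop. The documents do not support that. The withdrawal instruction in Appendix 1 sits under an opening sentence that limits it to the criteria in 5.3.4, and this patient meets none of those. The appendix's own block for this ALT band allows dosing. Only the bracketed tag and the SAE bullet point the other way. That objection stands in full: Appendix 1 is inconsistent with itself as well as with 5.3.4, and it does not plainly order withdrawal.

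The INR phrase could also be leftover text. INR appears in Appendix 1 only in one heading and its footnote, is not a required test, and is missing from all five criteria in 5.3.4. This is possible. Against it, the footnote with its anticoagulant exemption is repeated in Section 7.1.4(g), which also asks for any measured INR to be recorded on the SAE form. That suggests an intended arm, though it does not prove one.

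Finally, there are backstops. Section 5.3.8 lets the investigator stop for significant laboratory changes. Section 6.4.4 requires notice to the medical monitor when an unscheduled result is judged clinically significant. Appendix 1 requires notice within 24 hours for this ALT band. The text in 5.3.4 is a permission, so a site that stops breaches nothing. These points stand and limit the consequence; they do not make the texts agree.

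**Conclusion.** The inconsistency holds and is minor. Appendix 1 labels ALT ≥3xULN with INR >1.5 as criterion 1 and an SAE, while 5.3.4 and both permission paragraphs carry no INR condition. A patient in the narrow band shown above falls under a stopping-criterion and SAE heading, yet may go on being dosed.

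The reach is very small: an unscheduled test, one ALT band, no symptoms, 6 days of dosing, and several backstops. It does not touch the dose-escalation rules for CRS or EBV. SAP Section 2.3 records that the escalation stopping criteria were met in Cohort 3, so the remaining value may lie mainly in classifying any such recorded event and in reuse of this text.

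The conclusion rests on the wording of 5.3.4 and Appendix 1 as read. The Appendix 1 flow diagram was not available. It might show which rule was meant, but it would not remove the difference in wording.

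**What to change.** In Section 5.3.4, extend criterion 1 with an alternative: ALT ≥3xULN and INR >1.5, if measured, not applicable to patients on anticoagulants. In the permission paragraphs of 5.3.4 and Appendix 1, add the condition that INR is ≤1.5 if measured. Confirm that Section 7.1.4(g) carries the same arm.

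Deleting the INR arm from the Appendix 1 heading would also restore consistency, but it would drop a safeguard that the sponsor wrote in.

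The cost is protocol wording only. No test is added to the schedule. At most, an unscheduled INR above 1.5 would lead to a rare extra treatment stop.
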